## Program Summary

Study Name	Efficacy and Safety of Chinese Medicine in the Treatment of Chikungunya Fever: A Real-World Observational Study
Purpose	1. To explore the epidemiological characteristics and Chinese medicine syndrome distribution of Chikungunya fever; 2. To evaluate the effectiveness and safety of Chinese medicine in the treatment of Chikungunya fever.
Overall Design	A prospective observational study design based on real-world data
Sample size	Routine observation: all patients that can be collected during the observation period.
Diagnostic criteria	Suspected or confirmed cases of Chikungunya fever were included based on the diagnosis criteria of Chinese Guidance of the Diagnosis and Treatment for Chikungunya Fever (2017 Edition) published by the Chinese Center for Disease Control and Prevention.
Inclusion and exclusion criteria	
Inclusion Criteria
 

(1) Meets the suspected or confirmed diagnostic criteria for chikungunya fever;

(2) Symptom onset <math>\leq</math>3 days before enrollment;

(3) Actual prescribed treatment aligns with the study's group assignment (Chinese medicine, Western medicine, or combined therapy);

(4) Sign the informed consent form.

 
Exclusion criteria
 

(1) Severe chikungunya fever;

(2) Participation in another drug clinical trial within the past 3 months;

(3) Any other condition deemed by the investigator as unsuitable for enrollment.

Observation Grouping	Chinese medicine group: Patients receive only Chinese medicine treatments, which may include herbal formulas or acupuncture, tailored to their syndrome differentiation (e.g., heat-clearing, detoxifying, or dampness-resolving therapies); Western medicine group: Patients receive only standard Western medical care, which may include antipyretics (e.g., acetaminophen), NSAIDs for pain, and supportive treatments (e.g., hydration); Integrated Therapy Group: Patients receive both Chinese and Western treatments.
Observation period Visit	Maximum observation period: 28 days Visit time: Screening period/baseline: First visit D0, with lab assessments: complete blood count, CRP, and chikungunya nucleic acid tests; Treatment observation period: D1-D5, daily follow-up with clinical and lab assessments,

	D5 or before discharge: complete blood count, CRP, and chikungunya nucleic acid tests; Follow-up after treatment; telephone follow-up on D7, D14, and D28.
General information and medical history	1. Demographic information: gender, age, height, weight, ethnicity, etc.; 2. Medical history: past medical history, current medical history, epidemiological history and allergy history.
Effectiveness evaluation	

1. Joint Pain and Swelling Relief Rate (DAS44 Score)

2. Change in Rash Severity (Modified EASI Score)

3. Time to Complete Fever Resolution

4. Time to Viral RNA Clearance (RT-PCR Negative)

5. Recovery of Laboratory Markers

6. Time to Symptom Recovery

7. Incidence of Complications

Safety evaluation	Incidence of adverse events/adverse reactions.

**Flow chart**

Stage	Screening Period / Baseline	Treatment observation period							Follow-up after treatment (telephone follow-up)		
		Visit 1 D0	Visit 2 D1	Visit 3 D2	Visit 4 D3	Visit 5 D4	Visit 6 D5	Visit X Before discharge	Visit 7 D7	Visit 8 D14	Visit 9 D28
Visit point (D, day)											
Informed consent form	×										
Chikungunya RNA test	×						×	×			
Epidemiological data	×										
General information and medical history	×										
Physical examination, vital signs	×				×		×	×			
Body temperature	×	Patient diary card for body temperature record									
Chikungunya Symptom Scale	×	×	×	×	×	×	×	×	×	×	×
Complication		×	×	×	×	×	×	×	×	×	×
Severe / critical illness		×	×	×	×	×	×	×	×	×	×
Laboratory tests	×						×	×			
Patient diary card collection	×						×	×			
Medication records	×	×	×	×	×	×	×	×			
Adverse Events		×	×	×	×	×	×	×	×	×	×

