### 5 Observation Cohorts and Treatments

#### 5.1 Treatment Allocation by Cohort

- Chinese Medicine Group: Chinese treatments, which may include herbal formulas (e.g., decoctions, granules) or acupuncture, tailored to their syndrome differentiation (e.g., heat-clearing, detoxifying, or dampness-resolving therapies).;

- Western medicine group: Patients receive only standard Western medical care, which may include antipyretics (e.g., acetaminophen), NSAIDs for pain, and supportive treatments (e.g., hydration);
- Integrated therapy group : receive both Chinese and Western treatments.

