## 5.2 Observation period and follow-up

Maximum observation period: 28 days

Visit time:

Screening period/baseline: First visit D0, with lab assessments: complete blood count, CRP, and chikungunya nucleic acid tests;

Treatment observation period: D1-D5, daily follow-up with clinical and lab assessments, D5 or before discharge: complete blood count, CRP, and chikungunya nucleic acid tests;

Follow-up after treatment; telephone follow-up on D7, D14, and D28.

On D0, D5 or before discharge, collect 8 ml of whole blood (anticoagulant tube) for storage.

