## 7.2 Recording of adverse events

The name, severity, time of occurrence, duration, treatment measures, and process of treatment of adverse events, important adverse events, and adverse reactions that occur from the beginning of the treatment period to the last visit should be recorded in the research medical record, and their relevance to the trial drug should be evaluated based on comprehensive consideration of comorbidities and concomitant medications, and recorded in detail by the researcher.

When adverse events or adverse reactions are found, researchers can determine whether to discontinue observation based on the patient's condition. Cases in which medication is discontinued due to adverse events or adverse reactions should be followed up and the results recorded in detail.

If any abnormality is found in the safety test indicators such as vital signs, physical examination, complete blood count, urine routine, liver function, kidney function, electrolytes, etc. during or after treatment, the test must be repeated at an appropriate time and comprehensively analyzed with the subjects' onset and treatment to determine whether it is related to the test drug.

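### No medication record is scheduled after D5/discharge, although symptoms, complications and adverse events are collected to D28

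*Protocol*

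**What the plan says.** The Protocol flow chart is the only visit-by-visit schedule. Its row "Medication records" is marked at baseline, through the daily visits to D5 and at the visit before discharge, and is empty in the three telephone columns. The rows "Chikungunya Symptom Scale", "Complication" and "Adverse Events", and the row for severe or critical illness, are marked in all three.

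Section 5.2 sets "Maximum observation period: 28 days" and plans "telephone follow-up on D7, D14, and D28".

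Section 5.1 defines the Western cohort by exclusivity: "Patients receive only standard Western medical care". The Program Summary defines the Chinese medicine cohort in the same exclusive way. Neither definition carries a time limit, and no section fixes the day on which treatment ends.

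Section 7.2 has adverse events recorded up to the last visit and relatedness to the drug judged "based on comprehensive consideration of comorbidities and concomitant medications". Section 7.4, with its Tables 1 and 2, adds the time relationship and the dechallenge and rechallenge results as criteria.

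**The concern.** The study compares groups formed by what patients actually receive, and section 11 says it does not interfere with their treatment. A patient in a single-modality cohort may therefore add the other modality once home. With no medication question at the calls, outcomes from D7 to D28 would be reported under the initial cohort with no systematic way of seeing how many patients changed.

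Safety has a parallel problem. An event first reported at the D14 or D28 call has to be classified by timing, dechallenge and concomitant drugs, yet the schedule supplies no start or stop dates after D5/discharge. The adverse-reaction incidence, a stated safety outcome, is built from those classifications.

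This is not something an analysis plan can repair. Section 9.1.4 relies on multivariate and propensity-score methods, and neither can adjust for later treatment that was not recorded.

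**Working it through.** The protocol gives no figure to reproduce here, so the check is a reading of the schedule plus one proportion.

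**1. Flow-chart rows.** Each row has 11 cells in the extracted text.

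| Row | Cells marked | D7, D14, D28 |
|---|---|---|
| Medication records | 1 to 8 | blank |
| Symptom scale | 1 to 11 | marked |
| Complication | 2 to 11 | marked |
| Adverse events | 2 to 11 | marked |
| Laboratory tests | 1, 7, 8 | blank |

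The extracted header has 10 visit labels against 11 cells, which is an extraction fault. The laboratory row settles the alignment: sections 3.2 and 5.2 place those tests at D0 and at D5 or discharge, so cells 7 and 8 are D5 and the pre-discharge visit, and the last three cells are the calls. Three of the ten visit columns (nine numbered visits plus the pre-discharge visit) therefore have no medication record.

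**2. Share of follow-up without a scheduled record.** Share = (28 − day of last record) / 28. The discharge day is not in the protocol; D7, D10 and D14 are assumptions that show the range.

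| Last record | Days without record | Share |
|---|---|---|
| D5 | 28 − 5 = 23 | 82% |
| D7 (assumed) | 28 − 7 = 21 | 75% |
| D10 (assumed) | 28 − 10 = 18 | 64% |
| D14 (assumed) | 28 − 14 = 14 | 50% |

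**3. Other sections that might fill the gap.**
- Section 6.1(4) lists concomitant drugs with purpose, method and time, but under clinical characteristics and without naming a visit.
- Section 4.6 asks for the time of last medication, for dropouts only.
- Section 7.2 prompts an enquiry about drugs, but only once an adverse event has been reported.

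None of these schedules a record for all patients after D5/discharge.

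**4. Which outcomes are exposed.**
- Little affected: DAS44-CRP (CRP is drawn at D0 and D5/discharge), rash (compared on days 3 and 5), fever (diary cards collected by D5/discharge), RNA, and white-cell and platelet recovery (sampled at D0 and D5/discharge).
- Affected after D5/discharge: single-symptom and overall symptom-disappearance times, complications (counted from the start of treatment with no earlier cut-off), and adverse events and reactions.

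**The case against.** The strongest reply is that cohort membership does not depend on later medication. Section 4.4 assigns patients by actual prescription, inclusion criterion 3 requires the prescribed treatment to match the group, and the calls fall in a phase labelled as coming after treatment. On this reading the study compares initial strategies, and later add-on therapy is part of each strategy's course. That is a fair reading and it stands: the initial cohort label remains valid. It does not remove the need to describe what patients took afterwards. The phase label fixes no end of treatment, and without records the assumption that treatment has stopped cannot be verified.

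A reader might infer more than the protocol supports, in four ways:
- **That the effectiveness comparison as a whole is compromised.** It is not; the three outcomes in bold type (joints, rash, fever) rest largely on data to about D5/discharge.
- **That late adverse events will be judged with no drug history.** Exposure to D5/discharge is recorded, and section 7.2 obliges the investigator to consider concomitant drugs for each event. What is missing is a scheduled record behind that judgement, and any prompt for patients without an event.
- **That 82% of follow-up is always unrecorded.** This ignores the pre-discharge visit.
- **That a true difference shrinks in proportion to the share who switch.** Adding the other modality yields integrated therapy, not the comparator; symptoms already resolved by D5 cannot be affected; and switching driven by persistent symptoms could bias in either direction.

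**Conclusion.** The point holds as a gap in the data-collection schedule. Changes of modality after D5/discharge have no scheduled record, and neither do the drug dates needed to judge late events under sections 7.2 and 7.4. The unrecorded span is 23 of 28 days if the last record is D5, falling to half of follow-up if discharge is assumed at D14. The consequences are confined to symptom-disappearance times, complications and adverse events or reactions after D5/discharge. The protocol gives no switching rate and no basis for one, so neither the size nor the direction of any bias can be stated. The change is still worth making, because exposure not asked about at the time is hard to recover later and the calls are already planned.

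**What to change.** Mark the medication row of the flow chart at D7, D14 and D28. At each call ask one question: which Chinese and Western treatments the patient has used since the last contact, with start and stop dates. State in section 6.1(4) that concomitant medication is collected at those contacts, so that it agrees with the chart and with section 7.2.

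Keep patients in their initial cohort for the main comparison. Report how many changed or added a modality, and flag them in a descriptive or sensitivity analysis of the outcomes after D5/discharge. Do not simply censor them at the change: if patients with persistent symptoms are the ones who switch, censoring is informative and would bias the Kaplan-Meier and log-rank results planned in section 10.

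The cost is one more eCRF item on three existing calls, with some recall error by telephone.

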## Program text

### 1 Background

Chikungunya fever is an acute infectious disease caused by chikungunya virus (CHIKV), transmitted by Aedes mosquitoes, and characterized by fever, rash, and joint pain. The first outbreak of chikungunya fever was confirmed in Tanzania in 1952, and the virus was isolated in 1956. The disease is mainly prevalent in Africa and Southeast Asia. Since 2004, outbreaks of chikungunya virus have become more frequent and widespread, partly because the virus has adapted to make it easier to spread through Aedes albopictus, and people of all ages are susceptible. In areas where Aedes mosquitoes exist, when Aedes mosquitoes reach a certain density and natural conditions are suitable, if CHIKV is introduced, it may cause an epidemic or outbreak.

On July 8, 2025, an imported case of Chikungunya fever occurred in Foshan, Guangdong. Till July 19th, there have been a total of 1,873 confirmed cases had been reported in Foshan. The rapid spread of the epidemic has brought certain treatment pressures to medical institutions. At present, there are no available vaccines or specific drugs in China, and the clinical treatment plan is mainly symptomatic treatment. In order to effectively respond to the recent surge in Chikungunya fever patients in medical institutions, the Chinese medicine expert team of Guangdong has discussed and formed a Chinese medicine agreement formula plan and applied it in clinical practice. In order to evaluate the effectiveness of this plan, this observational study is planned to be carried out.

### 2 Purpose

- (1) To explore the epidemiological characteristics and Chinese medicine syndrome distribution of Chikungunya fever;
- (2) To evaluate the effectiveness and safety of Chinese medicine in the treatment of chikungunya fever.

### 3 Overall study design

Prospective observational study design based on real-world data.

#### 3.1 Sample size

Routine observation: all patients that can be collected during the observation period.

Maximum observation period: 28 days.

#### 3.2 Visit

Screening period/baseline: First visit D0, complete blood count, CRP, chikungunya nucleic acid and liver and kidney function tests

Treatment observation period: D1-D5, daily follow-up, filling in the CRF, collecting the complete blood count, CRP, and Chikungunya fever nucleic acid results on D5/Discharge day.

Follow-up after treatment; telephone follow-up was conducted on D7, D14, and D28.

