#### ■ VAS (Visual Analog Scale) pruritus score

No itching at all 0--1--2--3--4--5--6--7--8--9 — 10 Worst itching point

**(3) Complete fever reduction time: Complete fever reduction is defined as the body temperature dropping to 37.2°C or below after the first dose and maintained for 24 hours or more;**

(4) Nucleic acid negative conversion time;

(5) Time for single symptom to disappear;

(6) Overall symptom disappearance time;

(7) Time for white blood cell count to return to normal: the time from the first dose to the first observation of white blood cell count returning to normal;

(8) Time for platelet count to return to normal: the time from the first dose to the first observation of platelet count returning to normal;

(9) Incidence of Chikungunya-related complications: Proportion of patients with recorded AEs for Chikungunya-related complications (shock, DIC, encephalitis, acute liver injury, acute kidney injury, myocarditis, pericarditis, pneumonia, respiratory failure, rhabdomyolysis, acute pancreatitis) after the start of treatment.

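### RNA clearance and WBC/platelet recovery are time-to-event endpoints, but the named tests are scheduled only at D0 and D5/discharge, so Kaplan-Meier and log-rank largely reflect the test day

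*Protocol*

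**What the plan says.** **Endpoints.** Section 6.2 lists item (4), "Nucleic acid negative conversion time", without a rule for dating the event. Item (7) is "the time from the first dose to the first observation of white blood cell count returning to normal" and item (8) is "the time from the first dose to the first observation of platelet count returning to normal". For the two blood counts the event is therefore dated to the test day by definition; for RNA this is implied.

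**Sampling.** The protocol describes it in different ways:

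- Section 3.2: "collecting the complete blood count, CRP, and Chikungunya fever nucleic acid results on D5/Discharge day".
- Section 5.2: "D5 or before discharge: complete blood count, CRP, and chikungunya nucleic acid tests". The same sentence also promises "daily follow-up with clinical and lab assessments" on D1-D5, but names no test for D1-D4.
- Flow chart: the row "Chikungunya RNA test" and the laboratory row each carry three marks, read as baseline, D5 and a separate before-discharge visit.
- Sections 3.2 and 5.2: D7, D14 and D28 are telephone contacts, so no later sample is scheduled.
- Section 6.3: blood counts may also be collected as clinical practice dictates, with no fixed timing. RNA is not named there.

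**Analysis.** Section 10 prescribes Kaplan-Meier curves and medians, with log-rank comparison, for time-to-event variables. It uses two-sided tests at 0.05 and names no other method for times.

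**The concern.** Kaplan-Meier and log-rank take each event time as known. Here all that is known is that the change fell between the last positive or abnormal sample and the first negative or normal one. With one or two scheduled post-baseline samples, that gap can be the whole D0-D5 window.

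Two things follow. The reported median describes the visit schedule rather than the disease. And because groups are formed by actual prescription (section 4.4), discharge day may differ by treatment or hospital. A group tested earlier then has its events dated earlier, and log-rank can show faster clearance or recovery when the groups are identical.

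The problem is confined to items (4), (7) and (8). They come after the joint, rash and fever endpoints, which the protocol sets in bold.

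**Working it through.** The protocol gives no sample size, clearance rate or discharge-day distribution, so it has no figure of its own to reproduce. Every input below other than the sampling days D0 and D5 and the 0.05 level is an assumption made for illustration: exponential clearance with true median m, 100 patients per group, and early discharge testing at D3.

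**1. Everyone tested once, on D5.** The proportion negative by D5 is 1 − 2^(−5/m). All events are dated to day 5, so the Kaplan-Meier curve has a single step there.

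| True median m (days) | Negative by D5 | Kaplan-Meier median |
|---|---|---|
| 1 | 0.969 | 5 |
| 2 | 0.823 | 5 |
| 3 | 0.685 | 5 |
| 4 | 0.580 | 5 |
| 4.9 | 0.507 | 5 |
| 6 | 0.439 | not reached |

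A nearly fivefold range of true medians (1 to 4.9 days) gives the same answer. Log-rank then only compares proportions at D5. For medians of 2 v 3 days its simulated power is 0.60, against 0.62 from a two-proportion formula.

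**2. Test day differs between groups, clearance identical.** Take m = 3, one test per patient, 30% of group A tested at D3 and 70% at D5, and all of group B tested at D5.

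- Negative by D3: 1 − 2^(−3/3) = 0.50. Negative by D5: 0.685.
- D3: 200 at risk (100 + 100). Events: A 30 × 0.50 = 15, B 0. Expected in A: 15 × 100/200 = 7.5. Observed minus expected = +7.5.
- D5: 70 and 100 at risk, with the same event proportion in each, so observed minus expected = 0.
- Variance: D3, 15 × 0.25 × 185/199 = 3.49. D5, 116.5 events × (70 × 100/170²) × (53.5/169) = 8.94. Total 12.42.
- z = 7.5/√12.42 = 2.13. Rejection ≈ Φ(2.13 − 1.96) ≈ 0.57.

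Simulation gives 0.58. The whole signal arises at D3, where group B had no test and so could not have an event. At 30% v 20% the same steps give z = 2.5/√13.61 = 0.68 and rejection of about 0.10 (simulated 0.106).

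**3. Simulated log-rank false rejection** (4,000 runs; m = 2 / 3 / 4 days):

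| Tested early, A v B | One test only | Early patients retested at D5 |
|---|---|---|
| 30% v 0% (extreme) | 87 / 58 / 39% | 63 / 27 / 14% |
| 30% v 10% | 48 / 29 / 19% | 32 / 13 / 9% |
| 30% v 20% | 16 / 11 / 8% | 11 / 7 / 6% |
| 10% v 0% | 19 / 11 / 9% | 14 / 8 / 6% |
| 30% v 30% | 5 / 5 / 6% | 5 / 5 / 4% |

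A separate simulation with testing at D4 or D5 and m = 3 gave 12%, 35% and 88% when the D4 shares were 55% v 45%, 60% v 40% and 70% v 30%. With equal shares it gave 6%.

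**4. Candidate remedies.** An interval-censored proportional-hazards test rejected in 4-7% across the 30% v 0%, 30% v 20% and 30% v 30% settings (400 runs each; standard error about 1.1 points). When cleared patients were twice as likely to be tested at D3, it rejected in 4-8%; log-rank on those data rejected in 25-87%. Pooling D5 and discharge samples into one unadjusted proportion still rejected in 12-16% at 30% v 0% and about 6% at 30% v 20%.

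**The case against.** **The inflation depends on how the schedule is read.** The flow chart places the before-discharge visit after D5. If everyone is tested at D5 and those still positive are retested later (D6 to D8 assumed), log-rank rejects in about 5-6% even with unequal retest days. If everyone is tested only at D5, it is a valid comparison of proportions. This stands: the false-positive risk needs testing before D5 that is both common and unequal. But sections 3.2 and 5.2 allow a single sample at D5 or at discharge, and the uninformative median under D5-only testing does not depend on that risk.

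**Labs may be daily.** Read literally, section 5.2 says so, and the error would then shrink to about a day. Section 3.2 and the flow chart show no test on D1-D4, so the passages conflict and must be reconciled.

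**Extra samples and adjustment.** Unscheduled blood counts soften the problem for (7) and (8), but their timing is irregular and may also differ by group. The stratified and propensity methods of section 9.1.4 adjust for patient differences; they do not recover event times between samples.

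**This belongs in the SAP.** Section 10 does not name these endpoints, and interval-censoring detail is often left to an SAP. But the protocol itself fixes time endpoints, sparse sampling and the methods for times, and these do not fit together.

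**The large percentages are assumed.** True; they show direction and range, not an estimate for this study.

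**Conclusion.** The concern holds and should be corrected. From the schedule alone, with D5-only testing, the median for items (4), (7) and (8) can only be 5 days or not reached. Where discharge samples before D5 are used and their share differs between groups, log-rank's false-positive rate exceeds 5%. On the assumed inputs it runs from 6-16% for a 10-point difference in early testing (30% v 20%) to 9-48% for a 20-point difference (30% v 10%), across both retest rules and true medians of 2-4 days. With equal shares, or with everyone tested at D5 first, it stays near 5%. How often patients would be tested before D5 cannot be known from the protocol. The leading joint, rash and fever endpoints are not affected by this point.

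**What to change.** - For items (4), (7) and (8), replace Kaplan-Meier and log-rank in section 10 with an interval-censored analysis, using the interval from the last positive/abnormal to the first negative/normal sample.
- Alternatively, redefine these endpoints in section 6.2 as the proportion negative or normal at the D5 sample among patients positive or abnormal at D0. Handle patients sampled only at an earlier discharge by their actual sampling day or in a sensitivity analysis. Do not pool D5 and discharge samples into one unadjusted proportion.
- Reconcile sections 3.2 and 5.2, the Program Summary and the flow chart, so that it is clear whether there are one or two post-baseline samples and whether any laboratory test is scheduled on D1-D4.
- State as a limitation that discharge timing may depend on recovery, which standard interval-censored models assume away. Only a twofold dependence was simulated here.

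The cost is wording in the Program Summary, sections 3.2, 5.2, 6.2 and 10, and the flow chart if needed, with no extra samples. The price is that no precise median clearance or recovery time is reported, and the interval-censored result still relies on test days not depending strongly on recovery.
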